1. INTRODUCTION

1.1. Background

What is known

Idiopathic Immunoglobulin A nephropathy (IgAN) is the most common biopsy-proven glomerulonephritis in the world. It is more prevalent in Asia than in Europe and the US (1). IgAN is estimated to affect more than 500.000 people in Europe and it is the leading nephritis in kidney-biopsied patients. Approximately 40% of IgAN patients reach end-stage kidney disease (ESKD) 20 years after their kidney biopsy (2,3). The high prevalence of ESKD shows that IgAN has a significant economic impact in the countries because renal replacement therapy is costly. Moreover, the disease's onset in the second and third decades of life represents a social challenge because patients are typically very active and highly productive in the workplace. This challenge is one more reason to move from a generalized therapy for all patients to personalized therapy.

The first edition of the KDIGO guidelines, published in 2012 (4), suggested different therapeutic approaches for IgAN patients based on the clinical setting. Three sets of patients were considered:

i) *Patients with low risk* manifest minor urinary findings and proteinuria < 0.5 g/day, normal estimated glomerular filtration rate (eGFR) and normal blood pressure; they need only annual or biannual checks without therapy. They represent only 5-10% of the IgAN patient population.

ii) *Patients with intermediate risk* have proteinuria > 0.5 g/day with normal or reduced eGFR and normal or high blood pressure. They may benefit from continuous supportive therapy (renin-angiotensin system blockers; RASBs) when proteinuria lowers less than 1g/day, and eGFR remains stable. When proteinuria is > 1 g/day and eGFR (normal at baseline) declines to > 50 ml/min/ 1.73 m², after three months of continuous supportive therapy, patients may benefit from corticosteroids combined with supportive therapy for six months. When eGFR is less than 30 ml/min or between 30 and 50 ml/min/ 1.73 m², only supportive treatment is recommended with no immunosuppression, except for patients with rapidly progressive glomerulonephritis.

iii) *Patients at high risk* for acute or rapid loss of eGFR caused by rapidly progressive glomerulonephritis or nephrotic syndrome may benefit from corticosteroids combined with immunosuppressive agents and supportive therapy. These patients represent 2-5% of the IgAN population. In the presence of acute kidney injury (AKI) caused by red blood cells stacked in the tubules during the macrohematuria episode, only supportive therapy is suggested.

These indications have been confirmed in the recent edition of the KDIGO 2021 guidelines (5).

Unfortunately, the KDIGO guidelines could consider the presence of active and chronic renal lesions at the time of the kidney biopsy for therapy decision based on the lack of intervention evidence deriving from randomized trials. Nonetheless, such an approach would be supported, by the MEST-C score of the Oxford classification (6-8) validated in the VALIGA cohort (9). The MEST-C classification distinguishes active renal lesions (endocapillary proliferations (E) and extracapillary lesions C1-2) from chronic renal lesions (tubulo-interstitial damage T1,2).

In clinical settings, it is known that patients with active renal lesions are more prone to respond to immunosuppressive treatment than those with chronic lesions identified at kidney biopsy. In this

setting, approaching patients with chronic kidney lesions with immunosuppression may not be indicated, but this has not been formally explored in the setting of a randomized trial.

We have reviewed the effect of therapy (corticosteroids and/or immunosuppressive drugs) in biopsy-proven IgAN patients with active and chronic renal lesions based on cohort and registry data. Some of the most important publications have been listed in **Table 1** in which conclusions of the studies are reported. Retrospective and prospective clinical studies and meta-analyses show that corticosteroids and/or immunosuppressive therapy reduce the number of active renal lesions in repeated kidney biopsies (10-15). Moreover, there is an improvement in proteinuria and in kidney function (16-20). The same does not apply where chronic lesions are present.

Table 1. Retrospective and Prospective clinical studies, Systematic Reviews and Meta-analyses of randomized clinical studies promoting the benefit of corticosteroids and/or immunosuppressive therapy in reversing the active renal lesions and improving the renal prognosis			
Authors	Ref (no.)	Type of study	Conclusions
Shen XH et al.	10	Retrospective	IS reversed the active renal lesions (E1,C1,2), confirmed by repeat biopsy.
Moriyama et al	11	Retrospective	CS/IS improved the long-term renal prognosis of IgAN patients with E1, S1, C1 lesions.
Luo M et al.	12	Retrospective	Repeated kidney biopsies demonstrated that CS/IS reduce the number of crescents (C1,2).
Itami S. et al.	13	Retrospective	Presence of fibrinoid necrosis with crescents (C) or endocapillary (E) renal lesions is a pathological indicator of patients who may benefit from immunosuppressive therapy.
Tumulin JA et al.	14	Prospective	CS reduced proliferative lesions, proteinuria and stabilized renal function.
P. Yang et al.	15	Systematic Review	Patients with serious pathological changes (M1, S1 and T1,2) were more responsive to CS than patients with mild renal lesions (M0, S0, T0). E1 has better response to CS than T1,T2.
Tesar V et al.	16	Retrospective	CS reduced the risk of disease progression and proteinuria.
Guo Y et al.	17	Retrospective	Presence of fibrinoid necrosis with crescents (C) or endocapillary (E) renal lesions is a pathological indicator of patients who may benefit from immunosuppressive therapy.
Li Y et al.	18	Retrospective	Pulses of iv CS combined with low dose of prednisone is a new treatment option for high-risk IgAN patients.
P. Natale et al.	19	Systematic Review	CS therapy probably prevents decline in GFR or doubling of serum Creatinine (sCr) and proteinuria in adults and children with IgAN.
J. Tan et al.	20	Systematic Review	CS significantly delay the progression of renal damage with acceptable adverse events. They are recommended as the first line of immunosuppressive therapy.

CS: Corticosteroids; IS: Immunosuppressors

Referenced studies (10-15) seem to fit some of the Bradford Hill criteria (21) for the ascertainment of causality, specifically i) there are several observational retrospective studies (10-12) and a prospective study (14) and a systematic review (15) exploring the association between the type of kidney biopsy lesions and response to immunosuppressive treatment; ii) there is consistency across studies in the findings that active lesions may respond to immunosuppression as opposed to chronic lesions, data which have been identified by researchers from different countries in the world; iii) there is a strong association between different type of renal lesions and response to immunosuppressive therapy. In view of well established pragmatic clinical experience and the number, consistency and strength of the findings of observational studies, there seems to be scientific equipoise for the design and conduct of a randomized trial of interventions for IgA nephropathy based on the findings of kidney biopsy.

What is not known

There are no randomized data on the different treatment of active and chronic renal lesions in IgAN patients. The last RCTs using steroids (STOP IgAN and TESTING) (22,23) did not evaluate the type of lesions in the kidney biopsy at the enrollment time. Patients with active and chronic renal lesions all received the same treatment approach, independent of kidney biopsy findings. In consideration of this, recently, the researchers of the TESTING study have programmed a post-hoc analysis to evaluate the effect of therapy on renal lesions (24).

In STOP IgAN and TESTING studies, patients were enrolled after 3-6 months of RASB therapy, as per the current standard care. A recent histology study (25) based on two consecutive protocol kidney biopsies showed the dynamic changes of active and chronic renal lesions during the clinical course of the disease. Therefore, after 3-6 months active renal lesions not only in IgAN but in other glomerulonephritis (ie lupus nephritis) become chronic and corticosteroids may therefore not exert any role. This point has been commented by Troyanov et al (26) in a recent paper published by Itami et al (13) although needs to be formally explored in the setting of an experimental randomized trial.

Why this study

We have designed the CLlIgAN studies in which biopsy-proven IgAN patients with active and chronic renal lesions will receive different treatments in consideration of the above described points. Therefore, CLlIgAN is the first project including randomized studies which will take into consideration the type of renal lesions and patients will be enrolled separately in two RCTs based on the presence of active and chronic biopsy lesions.

Recently, oral sodium-glucose cotransporter 2 inhibitors (SGLT2i) were administered in patients with diabetic nephropathy type 2 and in other participants with chronic kidney disease (CKD), some of them were affected by IgAN (27-31). The effect of SGLT2i was compared with a placebo. All patients received RASB therapy. Patients with IgAN who received SGLT2i had a significantly lower risk of a composite end point (sustained decline of eGFR of at least 50%, ESKD, or death from renal or cardiovascular causes), independent of the presence or absence of diabetes (30,31). All patients had received kidney biopsy many months or years before the enrollment.

In CLlIgAN study the participants will receive for the first time Dapagliflozin after the kidney biopsy in presence of chronic or moderate renal lesions with high risk of CKD. This RCT will start on October 2022 when the drug will be available for all patients with CKD.

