To our knowledge, this is the first study in which corticosteroids are administered immediately after the kidney biopsy in IgAN patients with active renal lesions. Based on the existing evidence from randomized clinical trials, the KDIGO guidelines suggest in those cases: RASBs for 3-6 months and then corticosteroids in presence of persistent proteinuria and $GFR >30$ ml/min/1.73 m². This therapeutic approach, although supported by evidence, may be a challenge based on empiric clinical knowledge supported also by findings of cohort studies. This demonstrates that after 3-6 months active renal lesions become chronic and consequently no association may be found between exposure to corticosteroids and clinical response for IgAN patients. In our randomized clinical study we compare the standard approach proposed by KDIGO guidelines (RASBs for 3-6 months followed by corticosteroids) vs a novel approach consisting of early corticosteroid therapy combined with RASBs from the beginning.

CHRONIgAN TRIAL

Patients with chronic (T1,2) or moderate renal lesions (M0,1; S0,1, E0, C0, T0) will be enrolled in a two-arm trial with 1:1 allocation ratio to compare Dapagliflozin combined with RASBs (experimental arm) versus corticosteroids combined with RASBs (control arm) after 4 run-in months of RASBs treatment. The enrolled patients will have proteinuria ≥ 0.5 g/day and GFR ≥ 30 ml/min/1.73 m².

Participants will receive study treatments by 4 weeks from the kidney biopsy.

Patients assigned to the experimental arm will receive RASBs therapy (4 run-in months) followed by Dapagliflozin (10 mg /day orally) combined with RASBs for a total of 32 consecutive months. Patients assigned to the control arm will receive RASBs therapy (4 run-in months) followed by oral corticosteroids therapy (prednisone) for six months (0.4 mg/kg body weight for 2 months and then gradual reduction of 5 mg/day for 4 months) and then RASBs alone for a total of 36 consecutive months.

This is a parallel group, two arm, superiority trial with 1:1 allocation ratio.

Rationale of the study design

We decided the combination Dapagliflozin and RASBs because recently, SGLT2is were administered in patients with type 2 diabetes and in other participants with CKD (some of them were affected by IgAN) (29-31). In these studies, the effect of SGLT2is was compared with a placebo.

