4.2.2 Exclusion criteria

1. Non biopsy-proven IgAN
2. IgAN patients with minimal change disease at kidney biopsy and nephrotic syndrome.
3. IgAN patients with macrohematuria and acute renal failure.
4. IgAN patients with rapidly progressive glomerulonephritis (extracapillary lesions in more than 25 % of glomeruli in the kidney biopsy).
5. Patients with secondary IgAN (lupus nephritis, Schoenlein-Henoch purpura, liver cirrhosis).
6. Patients with superimposed IgAN in a kidney transplant.
7. Patients with other types of glomerular diseases
8. Patients with solitary kidney
9. Patients with end-stage kidney disease
10. Bleeding disorders not responsive to treatment
11. Patients with myocardial infarction or cerebrovascular stroke in the previous six months.
12. Severe liver diseases, infections, malignancies.
13. Uncontrolled diabetes (glycemia > 200 mg/dL and HbA1c $> 7.5\%$).

14. Aseptic necrosis of any bone.
15. Any prior immunosuppressive therapy.
16. Other morbidities that can be exacerbated by corticosteroids.
17. Previous adverse side effects and/or contraindications to RASBs and SGLT2is.
18. Pregnancy and breastfeeding.
19. If women of childbearing potential (WOCBP): patients not available to use highly effective contraceptive measures during the study treatment period and up to one month after the last dose of study drugs.

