4.3.2 Lifestyle modifications and other therapy

Concomitant therapy

Eradication of infectious foci, or concurrent antibiotic therapy to prevent infections or to avoid the transformation of a trivial infection into a severe complication will be considered. In presence of reduced kidney function ($eGFR < 30 \text{ ml/min/1.73 m}^2$) patients will receive reduced doses of nephrotoxic antibiotics.

Non-steroidal anti-inflammatory drugs and other nephrotoxic drugs will be avoided.

Due to the short term of corticosteroid therapy, IgAN patients will not receive supplementary therapy for osteoporosis. However, the physician will decide, in every patient, the supplementary therapy.

Inactivated pneumococcal and influence vaccines will be administered. Cotrimoxazole will be administered as *Pneumocystis jirovecii* prophylaxis.

COVID-19 Vaccine will be administered also in IgAN patients who will be enrolled in the arm of corticosteroids.

Patients treated with corticosteroids will receive ciprofloxacin before and during the two weeks following the meningococcal vaccination.

In presence of hypertension, anti-hypertensive drugs will be mainly replaced by RASBs to reduce hypertension and proteinuria.

Diuretics will be administered. Thiazides will be replaced by loop diuretics in presence of impairment of the renal function less than $30 \text{ ml/min/1.73 m}^2$.

Cardioprotective drugs will be administered in presence of cardiac insufficiency.

Statins will be prescribed in presence of hypercholesterolemia (> 200 mg/dL). Allopurinol will be administered in presence of hyperuricemia. It will be reduced if patients will have an impairment of the renal function less than 30 ml/min/1.73 m².

Cimetidine will not be prescribed because it interferes with serum creatinine measurements. Other gastroprotective drugs will be administered.

In presence of persistent or permanent eGFR <15 ml/min/1.73 m² patients will receive periodic hemodialysis or peritoneal dialysis.

Any other immunosuppressive therapies e.g. mycophenolate mofetil, cyclophosphamide or azathioprine will be not permitted in this study, unless there will be other definite indications for using these drugs.

Rifampin will be also prohibited from this study as it interacts with methylprednisolone and makes the study drug less effective.

Life style modifications

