6. SAMPLE SIZE AND STATISTICAL METHODS

ACIGAN. Data from the literature (22,23) have shown a difference in renal survival between corticosteroids and controls when the researchers assumed a difference of 50% in the primary end point (i.e. in the between-arms difference of delta 24 hour proteinuria from baseline to 6 months) as clinically relevant. Therefore, we assume that a mean delta proteinuria from baseline to 6 months in patients treated with RASBs alone (control arm) is 0.6 ± 1.0 g/24 hours (\pm SD) versus a mean delta proteinuria that is 1.2 ± 1.0 g/24 hours (\pm SD) from baseline to 6 months in patients treated with RASBs and corticosteroids (experimental arm). Based on these assumptions, we calculated a sample size of

132 patients (66 patients per group including a 10% dropout rate) for a power of 90%, a two-sided significance level of 0.05 and 3 years of recruitment. If the number of the enrolled patients will be insufficient, the recruitment period will be extended for two years.

CHRONiGaN. Data from the literature (29-31) have shown a difference of renal survival between SGLT2is and controls. There are no data in the literature exploring the difference of renal survival or proteinuria between SGLT2is and steroids. Here, the researchers assumed an opportunistic sample of 300 patients for this first comparative study (150 patients per group, including a 10% dropout rate).

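### CHRONIgAN randomises dapagliflozin, but no criterion excludes patients already on an SGLT2 inhibitor and the concomitant-therapy section does not address non-study use

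*Protocol*

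**What the plan says.** Section 3 describes CHRONIgAN in these words: "This is a parallel group, two arm, superiority trial with 1:1 allocation ratio". Dapagliflozin plus RAS blockers is compared with oral prednisone plus RAS blockers after four months on RAS blockers. Section 4.4 places the primary proteinuria endpoint at 10 months.

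On access to the drug, section 1.1 states "This RCT will start on October 2022 when the drug will be available for all patients with CKD". Section 4.3.1 adds that the study drugs are marketed products which the sponsor does not supply. Section 1.1 also says that "the participants will receive for the first time Dapagliflozin after the kidney biopsy in presence of chronic or moderate renal lesions".

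On eligibility, section 4.2.1.2 has no requirement that patients be SGLT2 inhibitor-naive. In section 4.2.2, exclusion 15 reads "Any prior immunosuppressive therapy". The only item naming SGLT2 inhibitors, exclusion 17, concerns earlier adverse effects or contraindications. Exclusion 13 removes uncontrolled diabetes only.

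On concomitant treatment, section 4.3.2 says "Any other immunosuppressive therapies e.g. mycophenolate mofetil, cyclophosphamide or azathioprine will be not permitted in this study", with an exception for other definite indications. It also restricts rifampin, NSAIDs and other nephrotoxic drugs, and cimetidine. SGLT2 inhibitors are not mentioned.

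On the assigned regimen, section 1.2 describes the run-in as RAS blockade alone, and sections 3 and 4.3.1 describe controls as on RAS blockers alone once steroids end.

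**The concern.** The exclusion of earlier immunosuppression protects one of the two randomised treatments. Nothing corresponding protects the other. A site screening a patient with controlled diabetes who tolerates an SGLT2 inhibitor finds that every criterion is met, alongside a run-in described as RAS blockade alone. Nothing tells the site how to reconcile the two.

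Two routes put the randomised drug class where the comparison assumes it is absent:

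- **Use at entry.** A current user assigned to dapagliflozin already has the drug's effect in the baseline value and shows little new fall. A current user assigned to control who continues receives steroid plus an SGLT2 inhibitor.
- **Start after entry.** A control in an open-label trial can obtain the drug outside the study. Section 1.5 foresees antidiabetic drugs, class unspecified, for steroid-induced hyperglycaemia.

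Sections 6.4 and 6.5 base the primary analysis on all randomised patients whatever their adherence, and section 6.2 stratifies by age and sex in centres, not by SGLT2 inhibitor use. Such patients therefore stay in the primary contrast.

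**Working it through.** **1. What the plan's own figures allow.** For ACIgAN the plan gives a control change of "0.6 ± 1.0 g/24 hours", an experimental change of 1.2 with the same SD, and a calculation "for a power of 90%, a two-sided significance level of 0.05 and 3 years of recruitment". This reproduces: n = 2(1.960 + 1.282)² × 1.0² / 0.6² = 58.4, so 59 per arm; 59/0.90 = 65.6, so 66 per arm and 132 in total.

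For CHRONIgAN, section 6 says only that "the researchers assumed an opportunistic sample of 300 patients for this first comparative study (150 patients per group, including a 10% dropout rate". The dropout arithmetic holds (150 × 0.90 = 135 evaluable per arm), but no effect size, SD or power is given. The protocol therefore offers no base from which to compute a loss.

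**2. Form of the bias.** Notation, none of it from the protocol:

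- D = fall in proteinuria due to dapagliflozin; S = fall due to steroids, assumed additive.
- b = share on an SGLT2 inhibitor at entry, equal in both arms by randomisation, who continue it.
- d = share of the remaining controls who start one and have its full effect by the endpoint.

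Change from baseline, leaving out the RAS-blocker effect common to both arms:

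- Experimental arm: (1−b)D
- Control arm: S + (1−b)dD
- Observed contrast: (1−b)D − (1−b)dD − S = rD − S, with r = (1−b)(1−d)

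The intended contrast is D − S. The shift is −(1−r)D, always against dapagliflozin.

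**3. Values of r (b and d assumed).**

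| b | d | r |
|---|---|---|
| 10% | 10% | 0.81 |
| 10% | 20% | 0.72 |
| 20% | 20% | 0.64 |

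**4. Effect on the contrast at r = 0.81 (D and S assumed, g/24 h).**

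| D | S | Intended D − S | Observed 0.81D − S |
|---|---|---|---|
| 0.8 | 0.4 | 0.40 | 0.648 − 0.4 = 0.248 |
| 0.6 | 0.6 | 0 | 0.486 − 0.6 = −0.114 |
| 0.4 | 0.8 | −0.40 | 0.324 − 0.8 = −0.476 |

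The first row loses part of a true advantage. The second creates a steroid advantage where none exists. The third exaggerates a real one.

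**5. Why no general sample-size multiplier follows.** The number of patients needed to detect the contrast changes by ((D−S)/(rD−S))². In the first row this is (0.40/0.248)² = 2.6; in the third it is (0.40/0.476)² = 0.7. The answer turns on D and S, which the protocol does not give.

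**6. Illustration of power only.** Borrow the ACIgAN SD of 1.0 and two-sided 0.05, with 135 per arm. The difference detectable with 90% power is (1.960 + 1.282) × √(2/135) = 0.395 g/24 h. If that is the true D − S and 1−r = 0.20, the contrast becomes 0.395 − 0.20D. For D = 0.4 this is 0.315 (power 0.73); for D = 0.8 it is 0.235 (power 0.49).

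**The case against.** The strongest defence is that the regimen itself is restrictive. A run-in on RAS blockers alone, and controls on RAS blockers alone after steroids, leave no place for an SGLT2 inhibitor. The rescue therapy in section 4.3.2 for this population is RAS blockers with prednisone. Section 4.7 lists non-compliance with study procedures as a ground for withdrawal. Enrolment falls within four weeks of the biopsy, and section 1.1 implies that general availability begins only at trial start, so few patients may be on the drug at entry. Concomitant medication is recorded at enrolment and follow-up visits (Figure 2B).

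Much of this stands. A reader might infer that controls are permitted an SGLT2 inhibitor throughout. The documents do not support that: such use is unmentioned in 4.3.2 and contrary to the described regimen. Substantial use at entry cannot be asserted either, since no figure is given. If sites stopped the drug at entry in both arms, the use-at-entry component would largely disappear.

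The defence does not close the gap. The regimen wording describes what patients receive as study treatment. It is not an eligibility criterion, a washout or an instruction about a drug prescribed elsewhere. The section 1.1 statement about first receipt of dapagliflozin is background, and may describe the novelty of the setting rather than drug-naive patients. Recording use measures it but does not prevent it.

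**Conclusion.** The gap is real and belongs to the protocol, since eligibility and concomitant-drug rules are not left to a statistical analysis plan. A current SGLT2 inhibitor user meets the CHRONIgAN criteria as written, and an intended restriction on non-study use is nowhere stated as one.

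The consequence is a shift of the estimate against dapagliflozin by (1−r)D, where r is 0.81 if 10% use the drug at entry and 10% of the remaining controls start it. This rests on additive effects, users continuing the drug, and assumed values of b and d. The actual size is unknown.

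Three stronger readings should be resisted:

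- **A simple pull towards no difference.** The comparator is active and only D is reduced, so a steroid advantage can be created or enlarged.
- **A fixed inflation of sample size, 1/r².** That would need the whole contrast to shrink by r, and CHRONIgAN has no power calculation to inflate.
- **The same defect in ACIgAN.** SGLT2 inhibitors are not randomised there, and randomisation balances background use in expectation.

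This is a cheap improvement worth making, not a demonstrated failure of the trial.

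**What to change.** In section 4.2.2, add for CHRONIgAN an exclusion of current SGLT2 inhibitor use, or of use within a period set by the sponsor before the baseline 24-hour urine collection.

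In section 4.3.2, state how non-study SGLT2 inhibitor use in the control arm is handled up to the primary endpoint, so that this section agrees with the RAS-blockers-alone wording in sections 1.2, 3 and 4.3.1. Which rule applies is for the sponsor to decide; the passages need to say the same thing.

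No new data collection is needed, since concomitant medications are already recorded. The cost is two short protocol edits and a slightly smaller recruitment pool, mainly patients with controlled diabetes who are already treated.
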